## Study Protocol and Statistical Analysis Plan

### C.1. Study Design

We will use a randomized single blind controlled trial design to address proposed aims. Specifically, the Center for Clinical Investigation (CCI) at Brigham and Women's Hospital will recruit adults aged 30+ years for participation in this study. In order to be eligible, a participant must be diagnosed with 1) type 2 diabetes at least one year prior to enrollment, 2) have elevated serum triglycerides (150-400 mg/dl), 3) a RHI  $\leq 2.0$ , and 4) be on statin treatment for at least six months at the time of enrollment. Additional eligibility criteria include a) ability to travel to the study site at Brigham and Women's Hospital for three study visits, the last two being spaced by 12 weeks, b) ability to provide informed consent, and c) willingness to abstain from fish oil and other forms of omega-3 supplements during the study period. Exclusion criteria include a) current eating disorders, b) pregnancy (using urine test for all premenopausal women of childbearing age without surgical sterilization), c) allergy to EPA or other omega-3 fatty acids, d) inability to provide informed consent, e) history or prevalent diagnosis of cancer, asthma, kidney insufficiency, stroke, or seizures, f) inability to provide blood specimens, g) current use of fish oil, >2 servings of fish per week, or omega-3 fatty acid supplements, and h) intention to move out of greater Boston area within one year. Complete list of inclusion and exclusion criteria is provided in Table 2.

**Table 2.** Inclusion and exclusion criteria

---

#### A. Inclusion criteria

- Age 30-75 years
- Hypertriglyceridemia (150-400 mg/dl)
- Statin use for at least six months at the time of screening
- Type 2 diabetes treated with diet and/or oral hypoglycemic agents diagnosed 1+ year from first visit
- Ability to provide informed consent and provide blood samples
- Willingness to abstain from fish oil, EPA, over the counter niacin, and other omega-3 fatty acid supplements during the study period (12 weeks)
- Ability to travel to the study site at Brigham and Women's Hospital for 3 study visits
- RHI of  $\leq 2.0$

#### B. Exclusion criteria

- Eating disorder or heavy drinkers (>2 standard drinks/d: a drink= 1.5 oz liquor, 4oz wine, or 12 oz beer)
- Treatment with chronic prescription pharmacotherapy for metabolic or cardiovascular disease management or risk factor modification (e.g., antihypertensive medications) that has not been stable for  $\geq 4$  weeks prior to screening
- Pregnant or lactating women
- Statin use <6 months at the time of screening
- Allergy to EPA, fish oil, shellfish, or other omega-3 fatty acids
- Current use of insulin, cyclophosphamide, estrogen, fibrates, niacin, hormone replacement therapy, testosterone, oral contraceptives, growth hormones, insulin-like growth factor-1, and other systemic steroids.
- Inability to provide informed consent or blood samples
- History or prevalent diagnosis of cancer, asthma, kidney insufficiency, stroke, seizures, allergic disorders, liver disease, or congestive heart failure
- Diagnosis of diabetes < 1 year prior to enrollment

- ❑ Intention to move out of greater Boston area within one year
  - ❑ Current use of omega-3 supplements, fish oil, or  $\geq 2$  servings of fish per week
  - ❑ Bleeding disorder or uncontrolled endocrine (i.e., thyroid) or metabolic disorders
  - ❑ Treatment with blood thinning drugs (i.e. warfarin and clopidogrel)
  - ❑ Major surgical operation 3 months before or after screening
  - ❑ Organ transplantation
  - ❑ Current participation in another trial or plan to do so during the study
  - ❑ Inability to give informed consent or to travel to the study center at Brigham and Women's Hospital
  - ❑ RHI of  $>2.0$
  - ❑ Triglycerides  $<150$  mg/dl or  $>400$  mg/dl
  - ❑ Body mass index of  $40+$  kg/m^2
- 

## **C.2. Recruitment of Study Subjects**

Upon receiving IRB approval from Brigham and Women's Hospital (BWH), potential participants will be recruited via usual advertisement techniques, including flyers posted on campus, media advertisement, and use of Partners Biobank (a letter co-signed by Partners Biobank PI and [name] with a card and a prepaid return address will be used). Each flyer will contain pertinent information summarizing the study protocol and objectives and contact information for study staff. Interested participants will contact the study coordinator, who will conduct a telephone screening for eligibility. Once a potential study subject has been determined to be eligible via telephone, he/she will be provided with detailed information about the study by the PI/study coordinator. The potential participant will then review the study materials before determining if he/she will voluntarily participate in the study. If yes, he/she will call the investigative team for an appointment for the first visit (screening) at the CCI, Brigham and Women's Hospital, Boston, MA. The goal would be to recruit and enroll 30 people with prevalent DM, triglycerides between 150 and 400 mg/dl, and current statin use. We will build in margin for 10% attrition and recruit 33 subjects overall. Details on inclusion and exclusion criteria are provided in **Table 2**.

## **C.3. Randomization Scheme**

Randomization will occur during the second study visit at the CCI for those who meet eligibility criteria. In this pilot study, 30 subjects will be randomized with equal probability to EPA intervention (n=15) or no EPA (no drug) (n=15) stratified according to gender. Permuted blocks (block size of 2) will be used to achieve groups of equal size. We will create blocks within each gender and each ethnicity (Caucasian, African- American, and others) to assure balance distribution of gender and ethnicity between the two groups.

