## **C.4. Study Visits**

**Visit # 1:** During this visit, the PI will explain the study objectives, study protocol, and sequences of events and answer any remaining questions that the subject may have about the study. If after such conversation with the PI, the subject is still willing to freely participate in the study, then he/she will sign the informed consent prior to the beginning of the screening process. Specifically, subjects will obtain overview of the study and the PI will complete endothelial function assessment using EndoPat2000 device. Subjects with RHI of 2.0 or less will be eligible and will be asked to provide blood sample for triglyceride measurement. First visit will end with the collection of blood specimen and subjects will be told that the coordinator will notify them via telephone of the results for further eligibility. Only subjects with triglycerides between 150 and 400 mg/dl will be eligible to be invited to the second study visit.

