**Visit # 3:** Subjects will be invited to come to the CCI fasting (starting from 8PM of the night before the visit) during the last visit, which will be 12 weeks after the second visit. Subjects will be allowed to take their morning medications prior to the visit. During the last visit, we will also complete count of any leftover pills among subjects randomized to EPA and repeat all study procedures conducted during the second visit.

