## **D.3. Statistical Power**

This is a pilot trial in which we will generate preliminary data to test the effects of EPA on endothelial function in DM subjects. The purpose of this study is to generate exploratory and hypothesis generating data, and most importantly, to estimate the effect size with standard error in order to determine the appropriate sample size with sufficient power for the future confirmatory trial. Assuming a standard deviation of 0.4 and 15 subjects per arm, we will have 80% power to detect an effect size of 1.05.

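### C.3 randomises only 30 (15 + 15), so the 10% attrition margin in C.2 (33 recruited) gives no cover after randomisation, and D.3's 80% power holds only if nobody is lost before week 12

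*Combined protocol and SAP*

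**What the plan says.** Section C.2 sets the target and the margin: "The goal would be to recruit and enroll 30 people with prevalent DM", with qualifying triglycerides and current statin use, followed by "We will build in margin for 10% attrition and recruit 33 subjects overall".

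Section C.3 fixes the timing and the number randomised: "Randomization will occur during the second study visit at the CCI for those who meet eligibility criteria", and "30 subjects will be randomized with equal probability to EPA intervention (n=15) or no EPA (no drug) (n=15) stratified according to gender".

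Section C.4 gives the sequence. Triglycerides are measured from the visit 1 sample, and "Only subjects with triglycerides between 150 and 400 mg/dl will be eligible to be invited to the second study visit". The final RHI is taken "during the last visit, which will be 12 weeks after the second visit". Table 3 places screening in weeks -4 to -1, randomisation at week 0 and the final measurement at week 12.

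Section D.1 makes the between-group comparison of change in RHI the primary analysis, under intention to treat. Section D.3 states: "Assuming a standard deviation of 0.4 and 15 subjects per arm, we will have 80% power to detect an effect size of 1.05".

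No section says that 33 are randomised, that subjects lost after randomisation are replaced, or how a missing week-12 RHI is handled.

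**The concern.** The same figure, 30, is the base for the attrition margin in C.2, the number randomised in C.3, and (as 15 per arm) the number behind the power statement in D.3. A margin for attrition normally ensures that the number entering the analysis is still adequate after losses. Here it stops at recruitment. With 30 randomised, the three extra recruits can replace only people who drop out before visit 2. They cannot replace anyone lost in the following 12 weeks, which is the longer interval and the one in which a loss removes a primary outcome.

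The 30 people described in C.2 already have triglycerides in range, and that is known only after visit 1. The margin is therefore added to subjects who have passed screening, so it does not look like an allowance for screen failure. Allowing for loss up to the final visit is its most natural purpose, and following C.3 as written would defeat it.

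What is at stake is modest: some power, and some precision in the effect estimate that the pilot is meant to supply for the confirmatory trial.

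**Working it through.** **Inputs from the documents.** 30 subjects as the goal, 10% attrition, 33 recruited (C.2). 30 randomised, 15 + 15 (C.3). SD 0.4, 15 per arm, effect size 1.05, power 80% (D.3). Two-sample t-test or Wilcoxon test on the change in RHI (D.1).

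**Assumptions.** Two-sided 5% t-test, because alpha and sidedness are not stated. Effect size 1.05 in SD units, because 1.05 raw RHI units with SD 0.4 would give power above 99.9%. SD 0.4 taken as the SD of the change in RHI. The documents give no loss rate after visit 2, so 10% is used for illustration and smaller losses are shown beside it.

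**1. The plan's own figures.**

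- Recruitment: 30 × 1.10 = 33. This reproduces.
- Power: noncentrality = d × √(n₁n₂/(n₁+n₂)) = 1.05 × √(225/30) = 2.876, with 28 degrees of freedom and critical value 2.048. Power is 79.3%, which agrees with the stated 80%. The effect detectable with exactly 80% power is 1.06 SD, or 1.06 × 0.4 = 0.42 RHI.

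**2. C.3 followed as written, with 10% lost after randomisation.** 30 × 0.9 = 27 analysed.

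- Split 14/13: noncentrality = 1.05 × √(182/27) = 2.726, with 25 degrees of freedom and critical value 2.060. Power is 74.5% and the detectable effect is 1.12 SD (1.12 × 0.4 = 0.45 RHI).
- Split 15/12: power is 74.1% and the detectable effect is 1.13 SD.

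**3. Smaller losses from 30 randomised** (mean power with losses spread at random over the arms).

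| Lost after visit 2 | Analysed | Power for 1.05 SD |
|---|---|---|
| 0 | 30 | 79.3% |
| 1 | 29 | 77.8% |
| 2 | 28 | 76.1% |
| 3 | 27 | 74.4% |

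If each subject had an independent 10% chance of loss, all 30 would complete with probability 0.9³⁰ = 0.04.

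**4. Precision.** The 95% confidence interval half-width is t × 0.4 × √(1/n₁ + 1/n₂). At 15/15 this is 2.048 × 0.4 × √(2/15) = 0.30 RHI. At 14/13 it is 2.060 × 0.4 × √(1/14 + 1/13) = 0.32 RHI.

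**5. All 33 randomised.** 33 × 0.9 = 29.7, so about 30 are analysed. From a 17/16 split with three lost at random, mean power is 79.1%, practically the figure that D.3 relies on.

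**The case against.** The strongest reply is that C.2 and C.3 describe different stages. Recruiting 33 and randomising 30 is coherent if all the attrition falls before visit 2: up to four weeks separate screening from randomisation, and C.4 adds a pregnancy test at visit 2. No section says that the 10% refers to loss after randomisation. This stands as far as it goes. A reader might infer a flat contradiction between the two sections, and the documents do not support that. But on this reading D.3 still assumes no loss over 12 weeks and does not say so. Intention to treat does not close the gap, because it cannot supply a week-12 RHI that was never measured, and no imputation is planned.

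The second reply is that the consequence is small. That also stands. The illustrative loss costs about five percentage points of power, in an exploratory pilot whose stated main purpose is to estimate an effect size and its standard error.

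A reader might also infer that an odd total such as 33 is itself a fault, given "Permuted blocks (block size of 2) will be used to achieve groups of equal size", and that 34 should be required. The documents do not support this:

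- They never say that 33 are randomised.
- Blocks of 2 are formed within gender and three ethnicity groups, which makes six strata. Each odd-sized stratum leaves one unpaired subject, so an even total does not guarantee equal arms either.
- Slight imbalance is harmless: 16/14 has 79.1% power against 79.3% for 15/15.
- 33 is a legitimate 30 × 1.10. Dividing instead (30/0.9 = 33.3, rounded up to 34) is a matter of convention.

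Nor do the documents show that a thirty-first eligible subject would lack an allocation. Lists blocked within strata whose sizes are not known in advance would normally hold more than 30 places.

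**Conclusion.** Wrong as written; minor, with moderate confidence. With 30 randomised, the C.2 margin covers none of the 12 weeks before the primary RHI, and D.3's power at 15 per arm is conditional on complete follow-up. At a 10% loss the shortfall is three subjects.

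A reader might infer that the D.3 calculation is itself mistaken. It is not: it is correct for 15 analysed per arm, and what is missing is the link from the number randomised to the number analysed.

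Confidence is moderate because C.2 does not say when the 10% attrition occurs. Reading it as including loss after visit 2 is an inference, though the more plausible one. The size rests on the assumed test, alpha and loss rate set out in the working.

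**What to change.** **Preferred.** Change C.3 so that all eligible subjects are randomised, up to the 33 already planned in C.2. That gives about 16 to 17 per arm, with about 30 expected to be analysed after 10% attrition by visit 3. D.3 can then stand, read as 15 analysed per arm. The cost is up to three more randomised subjects than C.3 now states, with their study drug where allocated and their visit 2 and visit 3 procedures. All of this is within planned recruitment. Visits, outcomes and the primary test do not change.

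**Alternative.** If the margin is meant only for loss before visit 2, say so in C.2 and restate D.3 for the number expected to be analysed, with the assumed loss rate given. For example, with 27 analysed: about 74% power for 1.05 SD, or 1.12 SD detectable with 80% power. This costs a sentence in each section and no additional subjects, but accepts the lower power.

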**Visit # 2:** Eligible subjects identified during visit # 1 will be asked to the CCI fasting but will be allowed to take their usual morning medications. Subjects will be instructed to start fasting at 8PM of the night before the study visit. Pregnancy test will be done to rule out pregnancy among pre-menopausal women without history of surgical sterilization. For subjects randomized to Vascepa, women who can become pregnant during the study will be asked to use a contraceptive method (i.e., hormone, intrauterine device, barrier, or abstinence) during the study and six months after the final visit. During the second visit, we will collect baseline blood samples (20 ml) for measurement of biomarkers (hsCRP, ET-1, and oxLDL); other relevant biomarkers (i.e., TNF $\alpha$ , NTproBNP, apoC3, apoA5, galectin 3, free fatty acids, relevant single nucleotide polymorphisms, and fatty acids will be measured at a later time upon securing new funding on stored blood specimens). Resting blood pressure and pulse will be measured (2x) after 15 minutes of rest and information on age, sex, race, education, height, weight will be collected. Subjects will also complete a Willett food frequency questionnaire to assess their baseline diet. Digital pulse amplitude measurements (see C.6. below) will be done. A dedicated research assistant (RA) will discuss the randomization scheme provided by the statistician with the subjects. The RA will not be blinded to the treatment assignment. Otherwise, PI, study coordinator, statistician, and other staff at the lab measuring biomarkers will all be blinded. Subjects randomized to Vascepa will know that they are taking the drug containing omega-3, since the drug is not disguised and there is no placebo (open label trial). The RA will advise subjects not randomized to Vascepa (control subjects) to continue their usual habits. Each subject randomized to EPA will receive a 12-week supply of study EPA from the BWH pharmacy with the instructions to take 4 g/d. Each subject will receive a study diary to record potential adverse effects during the next 12 weeks. Enrolled subjects will be contacted by telephone once a month by the coordinator to query about potential adverse effects and remind them of the upcoming final visit.

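### A fixed, published block size of 2 makes allocation predictable to anyone who knows earlier assignments, and the plan does not describe how allocation is concealed

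*Combined protocol and SAP*

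**What the plan says.** C.3 (Randomization Scheme) states the block size outright: "Permuted blocks (block size of 2) will be used to achieve groups of equal size". On strata it first says "30 subjects will be randomized with equal probability to EPA intervention (n=15) or no EPA (no drug) (n=15) stratified according to gender", then adds "We will create blocks within each gender and each ethnicity (Caucasian, African- American, and others". That gives two strata on the first sentence and six on the second. All are defined by characteristics that site staff can see or will record at visit 2.

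C.4 (Visit # 2) says that "the drug is not disguised and there is no placebo (open label trial", and that "A dedicated research assistant (RA) will discuss the randomization scheme provided by the statistician with the subjects". The RA is unblinded. The PI, coordinator, statistician and laboratory staff are to be blinded. The coordinator telephones enrolled subjects monthly about possible adverse effects.

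C.6 has the RA tell the subject the assignment only after all visit 2 activities are finished and the PI and other staff have left. Subjects are reminded not to reveal their group to anyone but the RA, and the RA collects bottles before blinded staff see the subject at visit 3.

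The plan does not say who holds the allocation list, whether the RA receives a list or single assignments, or when the RA first sees the next assignment.

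**The concern.** With blocks of 2, half of each completed block is determined in advance. The boundaries are also known, because every block has the same published length. A staff member who knows the order of subjects within a stratum and learns one assignment can deduce the other member of that pair.

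Two things are at stake. If the slip comes before the second member is randomised, the coming arm is known to someone who may still influence whether or when that person enters. If it comes later, two subjects are unblinded instead of one. The PI measures RHI at visit 3, and RHI is the primary outcome. D.3 says the pilot's main purpose is to estimate the effect size for a confirmatory trial, so either fault would reach the number the pilot is meant to deliver.

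**Working it through.** **The plan's own figure.** D.3 gives 80% power with 15 per arm at an effect size of 1.05 and SD 0.4. Alpha and sidedness are not stated; two-sided 0.05 is assumed. Reading 1.05 as standardised (1.05 × 0.4 = 0.42 RHI units), the two-sample t test gives 79.3% and the normal approximation 82.0%. The figure reproduces. The point does not depend on it, but it is used below to price the fix.

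**Certain assignments, fixed blocks of 2.** With n_s subjects in stratum s, the number fixed by the preceding assignment is the sum over strata of floor(n_s/2). If k strata have odd counts, this equals (N − k)/2.

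- Gender only, N = 30: k is 0 or 2, giving 15 or 14 of 30 (50% or 47%).
- Gender by ethnicity (six strata), N = 30: k is 0, 2, 4 or 6, giving 15 down to 12 of 30 (50% down to 40%).
- Six strata, N = 33 (the recruitment figure in C.2): k is 1, 3 or 5, giving 16 down to 14 of 33 (48% down to 42%).

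These bounds need no assumption about the mix of subjects.

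**Correct guesses.** Each certain assignment is guessed correctly, and each of the others with probability one half. With 12 certain: (12 + 18/2)/30 = 21/30 = 70%. With 15 certain: (15 + 15/2)/30 = 22.5/30 = 75%. Concealed allocation would give 50%.

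**Averages by simulation.** The documents give no gender or ethnicity mix, so 50/50 and 70/20/10 are assumed. With six strata, 45% of assignments are certain and guesses are right 0.45 + 0.55/2 = about 73% of the time. With gender only, 48% are certain.

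**Blocks of 2 and 4 mixed at random, same mix.** The observer knows all earlier assignments but not the block boundaries.

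| Six strata | Fixed 2 | Mixed 2 and 4 |
|---|---|---|
| Certain assignments | 45% | about 8% |
| Correct guesses | 73% | about 69% |
| Exact 15:15 | about 46% | about 38–39% |
| Within 16:14 | about 94% | about 87% |

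With gender strata only, certain assignments fall from 48% to about 10%.

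**Power at unequal arms** (t test, effect size 1.05): 79.3% at 15:15, 79.1% at 16:14, 78.6% at 17:13 and 77.6% at 18:12. The loss at 17:13 is 79.3 − 78.6 = 0.7 points.

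Blocks of 2 do not guarantee 15 per arm either. With six strata, up to six blocks can be left incomplete, so the arms can differ by as much as 6 (18 against 12).

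**The case against.** The strongest reply is that the people who could act on foreknowledge are meant not to have it. The coordinator screens by telephone and reports eligibility; the PI takes consent and measures RHI. Both are to be blinded. The RA, who does know assignments, has no stated part in scheduling, consent or eligibility, and discloses only after baseline work is complete. This stands, and it rules out two stronger readings.

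A reader might infer that allocation is not concealed. The documents do not establish that. They say the statistician provides a scheme that the RA discusses with subjects; they do not say it is a full list open in advance. What is established is that concealment is not described.

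A reader might also want to put a bias in RHI units on this. That would need an invented difference between steered subjects and complete steering by someone with no documented control over entry. Moreover, the primary outcome is change in RHI, so a difference in baseline level would not carry over one for one.

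It is also fair that very small strata give a balance reason for small blocks, and that varying the block size alone lowers guessing only from 73% to 69%.

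What the reply does not answer is leakage. C.6 controls when the subject is told, not when the RA knows. After visit 2, blinding of the coordinator and PI rests largely on subjects' discretion during monthly calls about adverse effects and at visit 3. Blocks of 2 double what each slip reveals.

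**Conclusion.** The point holds as a predictable scheme with undescribed concealment. For anyone who knows the earlier assignments in a stratum, 40–50% of assignments are certain under either reading of the strata. The averages of 45% certain and 73% correct guesses rest on the assumed mix. These figures describe full knowledge of past assignments; a blinded staff member gains only what leaks, two assignments per slip once both members of a pair are enrolled. The exposure affects both concealment and the blinding of the visit 3 RHI assessment. Its effect on the treatment estimate cannot be derived from the documents. The scheme should be changed because the remedy is cheap, not because bias has been shown.

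**What to change.** In C.3, replace the fixed block size of 2 with randomly varying sizes (for example 2 and 4) in the same strata. Keep the sizes out of the protocol and from all site staff.

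In C.4, have the BWH research pharmacy, which already dispenses the drug, hold the list. It should release one assignment at a time to the RA, after eligibility is confirmed and visit 2 measurements are complete. Because guess accuracy falls only to about 69% with mixed blocks, custody of the list matters as well as block size.

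The cost is a short amendment and a regenerated list, with no extra visits or subjects. Balance is slightly looser, as tabulated above, and the power loss is under 1 point at 17:13 or better.
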